11.6 Height and weight

The subject's height (without shoes) and weight will be recorded at V1 and V2, as listed in the flow chart.

11.7 Vital signs

Vital signs will include measurement of blood pressure and heart rate in a seated position (after ≥ 3 minutes of seated inactivity).

Significant findings that are present at screening must be recorded as medical history in the eCRF. Significant findings found at the following visits, which meet the definition of an AE, must be recorded on an AE page in the eCRF.

11.8 Lung function

The assessment of the lung function will include measurements of forced vital capacity (FVC), and FVC percent predicted, FEV₁ and FEV₁ percent predicted, for all subjects. Lung function measurements will be performed with a spirometer available at the clinic. FVC and the derived FEV₁ is measured as 3 valid measurements and the highest value will be entered in the eCRF.

Lung function will be measured according to the American Thoracic Society (ATS)/European Respiratory Society (ERS) spirometry recommendations (Reddel et al. 2009). The spirometry values will be reported by the site according to the site's pre-programmed spirometric reference equations. The reference equations and values used should be documented on every pulmonary function report.

11.9 Physical examination

The physical examination should be performed by a physician or designee (in accordance with local practice) and should be based on the following body systems:

Table 3 Physical examination

Organ system	Minimum examinations to be completed
General appearance	As applicable
Skin	Inspection of skin
Head	Ears - Inspection of auricles and external canal (otoscopy is not required) Eyes - Inspection of conjunctivae and eyelids Nose - Inspection of nasal mucosa (nasal endoscopy is optional) Oral cavity - oropharyngeal inspection of lips, tongue, tonsils and uvula will be performed for signs of mouth irritation, oedema, and any other abnormalities. When performed at visit 2, it will take place before IMP administration.
Lymph nodes	Examination of lymph nodes (cervical, axillary, and inguinal lymph nodes)
Respiratory	Auscultation/stethoscopy of lungs
Heart	Auscultation/stethoscopy of the heart.
Abdomen	As applicable
Urogenital	
Musculoskeletal and neurological	
Other abnormality	

Physical examination of optional body systems not performed should be marked as ND in the eCRF.

Significant findings that are present at screening must be recorded as medical history in the eCRF. Significant findings found at the following visits, which meet the definition of an AE, must be recorded on an AE page in the eCRF.

11.10 Oropharyngeal examination

At the oropharyngeal examination, the oral cavity and oropharynx, if possible, will be inspected for signs of mouth irritation, oedema, and any other abnormalities. Abnormal findings at visit 2 prior to first IMP administration should be recorded on the medical history. Abnormal or worsening of abnormal findings after first IMP dose are considered to be AEs.

Oropharyngeal examinations will take place before first IMP administration (V2). In case of any findings, dosing may need to be postponed, see section 9.2. Oropharyngeal examinations performed at V3 may be completed at any time during the visit.

11.11 Eosinophilic oesophagitis

At each visit to the clinic, subjects/parents/caregivers will be asked whether any of the following are present or have occurred since the last clinic visit:

- food impaction requiring medical intervention

- dysphagia/difficulty swallowing requiring the subject to drink large quantities of water to swallow food
- choking or gagging with meals
- persistent (8 weeks or more) dysphagia
- a sensation of food becoming lodged in the throat
- persistent (8 weeks or more) vomiting without evidence of infection
- persistent (8 weeks or more) early satiety
- unexplained weight loss in combination with other gastrointestinal symptoms

If a subject presents with any of the above, the investigator should consider referring the subject to a gastroenterologist for evaluation. If there is a clinical suspicion of eosinophilic oesophagitis, subjects must be referred to a gastroenterologist.

11.12 Pregnancy test

For female subjects of childbearing potential, a urine pregnancy test will be performed at all regular visits. For female subjects who have their first menstrual period during the trial, a urine pregnancy test will be performed at all subsequent visits. Further, the test will be performed during the trial, if a menstrual period is missed.

The urine pregnancy tests will be performed by dip-sticks at the trial site. If a pregnancy is confirmed the subject must be discontinued, please also refer to section 12.3.7 for reporting of pregnancy.

11.13 Skin prick test

SPT must be performed according to the procedure provided by ALK.

No data are available for SPT in pregnant subjects, therefore the urine pregnancy test must be performed before SPT.

Subjects enrolled in the trial will be tested for:

Table 4 Skin prick test

Country	Allergen
All Countries	Positive control Negative control HDM – Dermatophagoides pteronyssinus HDM – Dermatophagoides farinae Cat – Felis domesticus Dog – Canis familiaris Mould – Alternaria alternata Grass – Phleum pratense Mugwort – Artemisia vulgaris Birch – Betula verrucosa

Some medication may affect the outcome of the SPT and should be washed out before performing the SPT. Concerned medications are listed below:

Table 5 Medications with a possible interference with skin prick test

Drug	Recommended washout period prior to performing SPT
Antihistamine 
Oral, intravenous or topical (skin)Long-acting (astemizole)	3 days 100 days
Tricyclic antidepressant medications and antidepressant medication with antihistaminic effects (e.g., doxapine, mianserine)	14 days
Antipsychotic medications with antihistaminic effects (e.g. chlorpromazine, levomepromazine, clozapine, olanzapine, tiroidazine)	7 days
Glucocorticosteroid ²⁸ 
Local application of ultra high and high potency²⁹ (on the skin area used for SPT)OralShort-acting parenteralLong-acting parenteral (intra-articular or intramuscular)	21 days 30 days 30 days 90 days
Pizotifene	7 days

11.14 Blood and urine sampling

The following blood samples will be drawn during the trial, adding to an approximate total blood volume of 5 ml:

Purpose	Approximate volume	Number of samples
Safety / Haematology	2 ml	1
Safety / Blood chemistry	2.5 ml	1
Approximate total volume	4.5 ml	

In case of technical issues with sampling and/or unscheduled visits additional samples may be drawn.

The following urine samples will be collected:

²⁸ Treatment with systemic prednisolone with daily doses below 20 mg should not be discontinued (Des Roches et al. 1996). Estimated equipotent doses 20 mg Prednisolone = 20 mg Prednisone = 100 mg Hydrocortisone (iv. or per oral) = 16 mg Methylprednisolone = 3 mg Dexamethasone

²⁹ Augmented betamethasone dipropionate 0.05%; clobetasol propionate 0.05%; diflorasone diacetate 0.05%; fluocinonide 0.1%; flurandrenolide 4 mcg per m2; halobetasol propionate 0.05%; amcinonide 0.1%; betamethasone dipropionate 0.05%; desoximetasone; halcinonide 0.1%

Purpose	Volume	Samples during the trial.
Safety/Urinalysis	10 ml	1
Pregnancy tests	N/A	At each visit (if applicable)

11.15 Laboratory assessments

All laboratory assessments will be performed centrally at one or more certified laboratories selected by ALK.

The clinical laboratory values specified below will be reported to the investigator by the laboratory and he/she must immediately review them for clinical significance and act accordingly.

Laboratory assessments are described in a separate laboratory manual that also details blood sampling and shipment procedures.

The following laboratory variables will be measured:

Haematology

Erythrocytes, haemoglobin, haematocrit, mean corpuscular volume (MCV), mean corpuscular haemoglobin (MCH), platelets, leukocytes, neutrophils, eosinophils, basophils, lymphocytes, and monocytes.

Blood chemistry:

Creatinine, blood urea nitrogen (BUN), total bilirubin, alkaline phosphatase, aspartate aminotransferase (AST)/serum glutamic-oxaloacetic transaminase (SGOT), alanine aminotransferase (ALT)/serum glutamic pyruvic transaminase (SGPT), lactate dehydrogenase (LDH), sodium, potassium and calcium.

Urinalysis:

pH, protein, glucose, ketone, urobilinogen, bilirubin, haemoglobin nitrite, leukocytes and specific gravity.

11.16 Solicited signs/symptoms

In order to aid the AE and concomitant medication reporting, subjects will be given a paper diary to fill in daily (See Appendix 4). The diary will be used by the subject to help remember details and dates, when discussing AEs and concomitant medication with the investigator at the telephone contact and at visit 3 (and unscheduled visits, if applicable).

The diary will be used to capture 15 pre-specified symptoms/signs, identified as potential local side effects of sublingual immunotherapy (Passalacqua et al. 2013):

- Food tastes different
- Mouth ulcer/sore in the mouth³⁰

³⁰ A mouth ulcer is a discrete, painful lesion affecting the lining of the mouth where the mucosa is eroded

- Swelling of uvula/back of the mouth
- Itching in the mouth
- Itching in the ear
- Swelling of the lips
- Swelling of the tongue
- Tongue pain
- Tongue ulcer/sore on the tongue³¹
- Throat irritation/tickle
- Throat swelling
- Stomach pain
- Nausea (feel like throwing up)
- Vomiting
- Diarrhoea

If the subject answers “yes” to any of the symptoms, listed in the diary, the subject must also fill in whether any medication was used to treat this symptom and what type of medication.

Subjects and their legal representative will be trained by the investigator or designee at V2 on the proper method to complete the diary. In addition, the subject will be instructed to report other symptoms, that are not part of the diary list, to the investigator. The reported symptoms will be discussed with the subjects and after medical evaluation by the investigator be reported as AEs on the AE form in the eCRF. The evaluation of the solicited signs/symptoms must be documented in the medical records.

When evaluating the diary together with the subject at V3 the investigator should identify use of medication reported on the diary and fill each use of medication into the eCRF linked to the relevant AE.

If any AEs are reported on several consecutive days, the investigator should mark the AE as “recurrent” and inquire about the approximate duration each day of these recurring AEs and enter this information into the eCRF (see section 12.3).

12 SAFETY

Information about AEs, whether reported by the subject, discovered by the investigator by reviewing diary records, detected through physical examination or other means, must be collected and recorded on the AE form and followed up as appropriate. Evaluation of AEs including severity, causality, outcome and seriousness assessments must be performed by a physician.

³¹ A tongue ulcer is a discrete, painful lesion affecting an area on the tongue, where the mucosa is eroded

Any AE occurring from the time the informed consent was signed by the subject and until the FU-TC must be recorded and reported on the AE page in the eCRF. This includes all AEs, even AEs occurring before the subject is administered the IMP and whether or not AEs are observed in connection with the trial assessments and conduct of the trial. TEAEs are defined as adverse events with start date on or after the time of first IMP administration and no later than 7 days after last IMP administration.

12.1 Definitions

12.1.1 Adverse events

An AE is any untoward medical occurrence in a clinical trial subject, and which does not necessarily have a causal relationship with the administered IMP.

An AE can therefore be any unfavourable and unintended sign (including e.g. a medication error), symptom, or disease, whether or not considered related to the IMP.

The following events should not be recorded as AEs:

- A pre-planned procedure, e.g. a surgical intervention, unless the condition for which the procedure was planned has worsened since the informed consent form was signed.
- Pre-existing conditions documented as medical history. However, any worsening in severity or frequency of a pre-existing condition during the clinical trial period must be regarded as an AE.

Events of special interest

Selected AEs will be considered events of special interest (ESIs). ESIs are events that are considered critical for the evaluation of the product's safety profile and for which additional data will be collected. ESIs for this trial are:

- Systemic allergic reactions including anaphylaxis³²
- Events treated with adrenaline/epinephrine
- Severe local swelling of the mouth and/or throat
- Eosinophilic oesophagitis

See Appendix 5 for definitions and aggregated preferred terms used to identify ESIs.

³² The definition of anaphylaxis (Sampson et al. 2006) includes any 1 of the following 3 criteria:

1. Acute onset of an illness (minutes to several hours) with involvement of the skin, mucosal tissue, or both (e.g., generalised hives, pruritis, or flushing, or swollen lips, tongue, or uvula) AND either respiratory compromise (e.g., dyspnoea, wheeze-bronchospasm, stridor, reduced PEF, hypoxemia) or reduced BP* or associated symptoms of end-organ dysfunction (e.g., hypotonia [collapse], syncope, incontinence)
2. Two or more of the following that occur rapidly after exposure to a likely allergen for the subject (minutes to several hours):
 - a. Involvement of the skin-mucosal tissue (e.g., generalised hives, itch-flush, swollen lips, tongue, or uvula)
 - b. Respiratory compromise (e.g., dyspnoea, wheeze-bronchospasm, stridor, reduced PEF, hypoxemia)
 - c. Reduced BP* or associated symptoms (e.g., hypotonia [collapse], syncope, incontinence)
 - d. Persistent gastrointestinal symptoms (e.g., crampy abdominal pain, vomiting)
3. Reduced BP after exposure to known allergen for the subject (minutes to several hours): low systolic BP* or greater than 30% decrease in systolic BP

*Low systolic BP is defined as less than 90 mmHg from 11 to 17 years.

12.1.2 Serious adverse events

An SAE is any untoward medical occurrence or effect that at any dose:

- Results in death
- Is life-threatening (this refers to an event in which the subject was at risk of death at the time of the event; it does not refer to an event that hypothetically might have caused death if it had been more severe)
- Requires in-subject hospitalisation, regardless of duration, or prolongation of existing hospitalisation
- Results in persistent or significant disability or incapacity
- Is a congenital anomaly or birth defect
- Is judged to be medically important (this refers to an event that may not be immediately life-threatening or result in death or hospitalisation, but may jeopardise the subject or may require intervention to prevent one of the other outcomes listed above)

12.1.3 Medication errors, including overdose, abuse and misuse of the IMP

The definition of an AE also covers medication errors and uses of the IMP outside what is foreseen in the protocol, including misuse and abuse of the product. If doses higher than the recommended dose are taken, whether intentionally or unintentionally, the risk of AEs may increase. This includes the risk of anaphylaxis or severe local reactions.

- Medication error: Any unintended failure in the medication treatment process that leads to, or has the potential to lead to, harm to the subject
- Overdose: Any cumulative dose taken in one day that exceeds the dose intended by this protocol, regardless of whether the dose has caused any AEs
- Abuse: Persistent or sporadic, intentional excessive use which is accompanied by harmful physical or psychological effects
- Misuse: Intentional and inappropriate use

See Appendix 5 for definitions and aggregated preferred terms used to identify medication errors, abuse and misuse of the IMP.

12.2 AE assessments

12.2.1 Severity

The severity of an AE is a clinical observation assessed by the investigator using the following definitions:

- Mild: Transient symptoms, no interference with the subject's daily activities
- Moderate: Marked symptoms, moderate interference with the subject's daily activities
- Severe: Considerable interference with the subject's daily activities, unacceptable

12.2.2 Causal relationship to IMP

The causal relationship between an AE and the IMP is assessed by the investigator using the following definitions:

- Possible: A reasonable possibility of a causal relationship between the event and the IMP.
- Unlikely: The event is most likely caused by a different aetiology than the IMP.

For SAEs assessed as unlikely related to IMP, the most likely alternative aetiology should be provided.

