Clinical trial protocol

Trial ID: MT-18

A 28-day, single-armed, open-label trial to evaluate safety of the house dust mite (HDM) sublingual allergy immunotherapy (SLIT) tablet in adolescent subjects (12-17 years of age) with HDM allergic rhinitis/rhinoconjunctivitis (AR/C) with or without asthma

Sponsor: ALK-Abelló A/S
[name]
[name]

Investigational medicinal product: HDM SLIT-tablet

Phase: III

Regulatory trial identifier number:
EudraCT No: 2020-000446-34

Document status: Final

Date: 8-Apr-2020

Version number: 2.0

Property of ALK

May not be used, divulged, published or otherwise disclosed without the written consent of ALK

Protocol synopsis

Trial ID	MT-18
EudraCT no.	2020-000446-34
Title of trial	A 28-day, single-armed, open-label trial to evaluate safety of the house dust mite (HDM) sublingual allergy immunotherapy (SLIT) tablet in adolescent subjects (12-17 years of age) with HDM allergic rhinitis/rhinoconjunctivitis (AR/C) with or without asthma
Short title	Open-label 28-day safety trial in HDM allergic adolescents
Main objective	The primary objective is to evaluate safety and tolerability of the HDM SLIT-tablet in adolescents (12-17 years of age) with 28 days of treatment
Primary endpoint	At least one treatment-emergent adverse event (TEAE)
Key Secondary endpoints	
At least one solicited TEAEAt least one IMP-related AEAt least one treatment-emergent serious adverse event (SAE)
Trial design	
A 28-day, single-armed, open-label, multi-centre trial in adolescent subjects (12-17 years of age) with HDM AR/C, with or without asthma.
 
The trial consists of three trial periods: a screening period (up to 12 weeks), a 28-day treatment period and a 1-week follow-up period.
 
Three in-clinic visits are planned for each subject: screening (visit 1), first dosing (visit 2), and a final visit (visit 3). In addition, a phone contact 7 days after visit 2 and a follow-up phone contact (FU-TC) approximately 7 days after visit 3 will take place.
 
During the treatment period a subject diary will be used to capture 15 pre-specified symptoms/signs daily and associated medication taken. The diaries are to be used for evaluation by the investigator when capturing AEs at visit 3.

Main assessments	Spirometry (FEV ₁), skin prick test (SPT)

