2.3 Secondary endpoints

- At least one solicited TEAE
- At least one IMP-related adverse event (AE)
- At least one treatment-emergent serious adverse event (SAE)

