13 EARLY TERMINATION OF TRIAL

ALK reserves the right to terminate the trial due to safety concerns.

If the trial is prematurely terminated or suspended, the investigator should promptly inform the subjects/legal representatives and ensure appropriate therapy and follow-up. Furthermore, the investigator and/or ALK should promptly inform the IEC and provide a detailed written explanation. The regulatory authorities should be informed according to national regulations.

Early trial termination may be the result of any single criteria specified below:

1. IMP-related death of an individual
2. IMP-related anaphylactic shock in at least 2 subjects³³ defined as:

Acute onset of an illness (minutes to several hours) with involvement of the skin, mucosal tissue, or both (e.g., generalised hives, pruritus, or flushing, swollen lips, tongue, or uvula) AND medically confirmed reduced BP with associated symptoms of end-organ dysfunction (e.g., hypotonia [collapse], syncope, incontinence).

Low systolic BP for children is defined as less than $70 \text{ mmHg} + (2 \times \text{age})$ from 1 to 10 years, and less than 90 mmHg for 11 to 17 years of age.

IMP intake may only be resumed after the information has been presented to regulatory authorities, and regulatory authorities concur with continued IMP intake. In case of complete premature IMP discontinuation, participating investigators/subjects/legal representative, the IEC, and the relevant regulatory authorities will be promptly informed.

³³ The criterion for 2 events is based on prior trial experience where it has been observed that events of severe anaphylactic reactions unrelated to IMP may occur in allergic subjects even with a temporal relationship to tablet administration.

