15.8.1 Evaluation of AEs

Below is the list of the safety endpoints in the trial:

Primary endpoint	At least one TEAE
Secondary endpoint	At least one solicited TEAE
Secondary endpoint	At least one IMP-related AE
Secondary endpoint	At least one treatment-emergent serious adverse events (SAE)
Other	At least one treatment-emergent systemic allergic reaction including anaphylaxis
Other	At least one TEAE treated with adrenaline/epinephrine
Other	At least one treatment-emergent severe local swelling or oedema of the mouth and/or throat
Other	A TEAE of eosinophilic oesophagitis
Other	A TEAE leading to discontinuation
Other	Daily duration of recurrent TEAEs

The different types of AEs (TEAEs, solicited TEAEs, IMP-related AEs, treatment-emergent SAEs, treatment-emergent systemic allergic reactions including anaphylaxis, TEAEs treated with adrenaline/epinephrine, treatment-emergent severe local swellings or oedemas of the mouth and/or throat, TEAEs of eosinophilic oesophagitis, and TEAE leading to discontinuation) in the above table will be summarised by system organ class (SOC) and preferred term (PT).

Summaries will include number and proportion of subjects having the event, as well as number of events. For the proportion of subjects with at least one events the exact 95% confidence interval will also be presented.

The different types of AEs mentioned in the above table will generally also be summarised according to severity, relationship to trial product, outcome, action taken, seriousness, and number of events leading to treatment discontinuation. However, in case of few events of the specific type, these details will be listed instead.

Duration of recurrent TEAEs will be summarised according to PT.

Most frequent AEs defined as those occurring in more than 2% of subjects will be summarised according to SOC and PT. Duration of most frequent AEs, as well as time to onset of most frequent AEs, will be summarised according to SOC and PT.

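### The two causality categories in section 12.2.2 overlap with no rule for which prevails, so the secondary endpoint on IMP-related AEs can be classified inconsistently

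*Combined protocol and SAP*

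**What the plan says.** Section 12.2.2 places the judgement with the investigator: "The causal relationship between an AE and the IMP is assessed by the investigator using the following definitions". Two definitions follow:

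- The first category asks only whether the tablet is a credible cause: "Possible: A reasonable possibility of a causal relationship between the event and the IMP"
- The second category asks instead which cause leads: "Unlikely: The event is most likely caused by a different aetiology than the IMP"

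The section adds one instruction: "For SAEs assessed as unlikely related to IMP, the most likely alternative aetiology should be provided".

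The classification feeds an endpoint. "At least one IMP-related AE" is a secondary endpoint in sections 2.3 and 15.8.1, and the synopsis lists it under "Key Secondary endpoints". Section 15.8.1 reports it as a proportion of subjects with an exact 95% confidence interval, and also tabulates AEs by relationship to the product. It does not say which category of 12.2.2 makes an event IMP-related.

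Two other places use relatedness: the reporting of SAEs that come to light after the follow-up call (12.3.8), and both early-termination criteria (section 13).

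**The concern.** Two categories that sort every event should be complements. Here one asks whether the tablet is a credible cause, and the other asks whether something else is the leading cause. Both can be true of the same event.

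Such events are foreseeable. The diary asks every day about stomach pain, nausea, vomiting and diarrhoea (11.16), all of which commonly have other causes. There is no control arm to show the background rate. With about 250 subjects at an estimated 20 to 30 sites, each site contributes roughly 8 to 12 subjects (250/30 = 8.3; 250/20 = 12.5), so different local readings would be hard to detect in the data.

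At stake is whether the IMP-related proportion means the same thing at every site, and whether it honours the reasonable-possibility standard that the protocol itself sets.

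**Working it through.** **Step 1: are the categories exclusive?** The plan attaches no figure to this point, so the check is logical. Cross the two tests:

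| Tablet a reasonable possibility? | Another cause most likely? | Category under 12.2.2 |
|---|---|---|
| Yes | No | 'Possible' only |
| Yes | Yes | Both |
| No | Yes | 'Unlikely' only |
| No | No | Neither (in practice empty: if the tablet is not credible, some other cause, known or not, must lead) |

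The second row is the defect. A reasonable possibility does not require the tablet to be the leading cause, so the row is not empty.

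**Step 2: does any text resolve it?** The instruction on SAEs asks for the alternative cause once 'Unlikely' has been chosen; it does not say when to choose it. Sections 2.3, 12.3.8, 13 and 15.8.1 use relatedness without referring to 12.2.2 and without a tie-break. That IMP-related means 'Possible' is implied only.

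**Step 3: what could it do to the estimate?** The documents give neither the share of subjects with a clearly related AE nor the share with overlap events. Both are assumptions here. Take n = 250 (15.1), x subjects with a clearly related AE, and a further share whose only candidate events fall in the second row. The exact 95% limits are the 0.025 quantile of Beta(x, n − x + 1) and the 0.975 quantile of Beta(x + 1, n − x).

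| Clearly related (assumed) | Overlap marked 'Unlikely' (95% CI) | Overlap marked 'Possible', share 2% | share 5% | share 10% |
|---|---|---|---|---|
| 100/250 | 40.0% (33.9 to 46.4) | 105/250 = 42.0% | 112/250 = 44.8% | 125/250 = 50.0% |
| 150/250 | 60.0% (53.6 to 66.1) | 155/250 = 62.0% | 162/250 = 64.8% | 175/250 = 70.0% |
| 200/250 | 80.0% (74.5 to 84.8) | 205/250 = 82.0% | 213/250 = 85.2% | 225/250 = 90.0% |

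(A 5% share is 12.5 subjects, rounded to 12 or 13.) At 2% the shift stays inside the sampling interval. At 5% it stays inside for the two lower base rates and sits at the upper limit for the highest. At 10% it lies outside for all three.

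**Step 4: how many overlap events would that take?** The endpoint is counted per subject, so only subjects without a clearly related event can move. If overlap events occur independently of clear ones, shift = share with any overlap event × (1 − base), so the required share = shift/(1 − base). At a 60% base, a 2-point shift needs 2/0.40 = 5% of subjects and a 10-point shift needs 10/0.40 = 25%. For a 10-point shift, the requirement is 10/0.60 = 16.7% at a 40% base and 10/0.20 = 50% at an 80% base. The documents do not show whether such shares are realistic.

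**The case against.** The strongest reply is that the labels are plainly opposed. Read with its label, 'Unlikely' covers events where another cause makes the tablet an improbable one, and a sensible investigator would treat the pair as a dichotomy. Data entry follows guidelines (section 14) that are not among the documents and might hold a precedence rule. This softens the point but does not remove it: the protocol text is what defines the endpoint, and that text lets both categories apply.

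Several limits on the consequences do stand:

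- Most safety endpoints do not use causality. The primary endpoint is any TEAE; solicited AEs are found by preferred term within the treatment period (Appendix 5); SAEs are defined by seriousness (12.1.2). Nausea, stomach pain, vomiting and diarrhoea are all solicited, so they count in another secondary endpoint whichever box is ticked. All AEs are also listed (15.8).
- Typical oral itching soon after intake will rarely be borderline.
- No hypothesis is tested, so no formal decision rule depends on the proportion.

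A reader might infer more than the documents support:

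- *That the endpoint is biased downwards.* An investigator who applies the 'Possible' wording literally pushes the count up. The text supports inconsistency, not a net direction.
- *That one classification decides early termination.* Section 13 says that termination may follow from its criteria, so they are discretionary. SAEs and events of special interest reach the sponsor within 24 hours whatever their causality (12.3.3).
- *That the section 13 footnote shows the overlap at work.* It says that "events of severe anaphylactic reactions unrelated to IMP may occur in allergic subjects even with a temporal relationship to tablet administration", to explain why two events are required. It does not say that those events also had a reasonable possibility of tablet causation.

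**Conclusion.** The point holds as a defect of definition. The categories in 12.2.2 are not mutually exclusive, no rule says which prevails, and IMP-related is not tied to either. The endpoint on IMP-related AEs and the relationship tables can therefore be classified differently by different investigators. Where the 'Unlikely' wording is followed literally, events that meet the reasonable-possibility standard drop out. Each event presumably receives one box, so nothing is counted twice.

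The size cannot be derived. The shifts in the table, from 2 points to 10, rest wholly on assumed shares, and the larger ones require a substantial fraction of subjects to have borderline events. The finding does not touch the primary, solicited-TEAE or SAE endpoints. It merits correction because a stated rule conflicts with its neighbour and feeds a secondary endpoint reported with a confidence interval, and because the correction is a matter of wording.

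**What to change.** - In 12.2.2, define 'Unlikely' as no reasonable possibility of a causal relationship between the event and the IMP, and add that 'Possible' applies whenever there is a reasonable possibility, even if another cause is more likely.
- In 15.8.1, state that IMP-related means assessed as 'Possible'.
- Reconcile the use of relatedness in 12.3.8 and section 13 with that definition, leaving the termination criteria themselves unchanged.
- Carry the same wording into the eCRF guideline.

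This needs no new data, visit or analysis. It has two costs. The IMP-related proportion may come out slightly higher. If the earlier trials used the current wording, which the documents do not say, the result will also be less comparable with the adolescent safety database that this trial is meant to supplement; the trial report should disclose this.
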